## **CHeRP IRB Additional Protocol Information:**

*In addition to the CHeRP SmartForms, all protocols must include the following sections. If a section is not applicable for the current protocol please indicate why this is the case. Please note that a complete protocol\* consists of the CHeRP forms and the information provided in this form.*

### **TITLE:**

Bilateral Continuous Erector Spinae Blocks for Post-Sternotomy Pain Management:  
A Single Arm Interventional Study.

### **A. Specific Aims/Objectives:**

**Overall Aim:** To evaluate the efficacy of bilateral continuous erector spinae blocks (BESB) for postoperative analgesia in children and adolescents undergoing cardiac surgical procedures via sternotomy in the Early Recovery After Surgery (ERAS) program in a single arm, open label, interventional study.

#### Specific Aims:

1. Evaluate the utility of BESB in cardiac surgical patients by assessing the pain scores, opioid consumption, and complications related to BESB.
2. Compare intra- and postoperative opioid use in patients receiving BESB vs. matched historical controls who did not receive BESB in the ERAS program.
3. Compare clinical outcomes between the 2 groups: duration of mechanical ventilation, time to mobilization, pain scores (median pain score per period), intensive care unit length of stay (LOS), incidence of postoperative nausea and vomiting, postoperative complications, hospital LOS, readmissions, mortality, recovery to baseline activity and sleep post discharge, total and rescue opioid pain medication requirements.
4. Evaluate quality of sleep and activity with (Fitbit™) smart watch device of patients receiving BESB during the postoperative period.

**Hypothesis:** The investigators hypothesize that BESB is efficacious with respect to pain control and will lead to a 15% or greater reduction of consumed opiate equivalents at 12, 24 and 48 hours, and the 24-hour period preceding both 72 and

96 hours postoperatively compared to matched historical controls who received standard of care pain management (systemic opioid therapy).

## **B. Background and Significance:**

Regional anesthesia—and pediatric regional anesthesia in particular—is a rapidly evolving subfield of anesthesia practice driven with considerable urgency by the growing recognition that even appropriate perioperative opioid administration can have significant deleterious long-term effects.

Regional anesthetics can provide targeted, continuous analgesia to select dermatomes with minimal additional patient risk and as such, have become routine components of opioid-sparing intraoperative and postoperative pain management plans for non-cardiac surgical patients at BCH. In addition to the postulated benefit of reducing overall opioid exposure (and potentially reducing the risk for long term physiologic and behavioral dependence upon opioids), regional anesthetics may allow for earlier extubation after selected surgeries, shorter intensive care unit (ICU) stays, shorter inpatient admissions, earlier mobilization, fewer gastrointestinal complications, and improved patient and care team satisfaction scores.

Historically, regional anesthetics have been avoided in cardiac surgery as most patients are pharmacologically anticoagulated during their procedures and are thus at increased risk for bleeding. This is particularly worrisome in the pediatric cardiac surgical population as many of these children remain intubated for an extended period of time postoperatively and therefore may not have reliable neurological exams in the setting of neuraxial regional anesthetics—potentially resulting in unrecognized hemorrhage-related acquired neurological deficits.

Recently, the erector spinae block (ESB) has become popular for providing analgesia after a number of anterior chest and abdominal procedures. This simple interfascial plane block can reliably provide unilateral chest and/or abdominal wall analgesia. It has been described in numerous case reports and case series as an effective block for management of unilateral thoracotomies, unilateral rib fractures, unilateral abdominal incisions and most notably, for management of post-sternotomy pain when applied bilaterally. New case reports and series involving the ESB are being published almost weekly with a growing number of manuscripts specific to cardiac surgical applications. Indeed, numerous randomized controlled trials have investigated the analgesic efficacy of bilateral erector spinae plane blocks (BESB) compared with

conventional treatment for pain after cardiac surgery in adult patients and have been published recently (2018-2019) with promising results.

As an interfascial plane block in a compressible anatomical space, the ESB is considered safe in anticoagulated (or recently anticoagulated) patients. It is fast becoming a preferred anesthetic option at BCH for anticoagulated patients - as opposed to neuraxial (e.g. epidural) and paraneuraxial blocks (i.e. paravertebral) nerve blocks, which are largely contraindicated in this setting. Further, given its relative ease of placement, apparent efficacy and safety profile, it is increasingly becoming a standard option for patients undergoing a wide range of thoracic, abdominal and thoraco-abdominal procedures.

We are fortunate at BCH to have the largest pediatric cardiac surgical program in the United States. We also have an active, and well organized regional anesthesia service. We are in a unique position to more thoroughly evaluate the effectiveness and safety of regional anesthetics in children following cardiac surgery. Furthermore, we feel it is critical that institutions such as BCH take a leading role in documenting the effects of regional anesthesia on the most important outcome measures when considering perioperative medicine. These include: overall pain management, surgical healing, functional recovery, long term pain symptoms, and emotional/behavioral outcomes after surgery.

Indeed, given these considerations, our group recently investigated the feasibility of performing these blocks bilaterally in a pediatric cardiac surgical population undergoing sternotomy-based procedures (IRB-P00031524). At the conclusion of this 10-patient pilot, our group found that performing these blocks was technically feasible, requiring 30 minutes or less of OR time, resulting in no known complications. Furthermore, our data suggested an approximate 25% reduction in rescue opioid requirements in the first 48 hours amongst the erector spinae group ( $p=0.048$ ).

During the short time required to complete our pilot study, several additional adult studies of improved size and quality have been published demonstrating favorable outcomes with this block for a variety of indications, including post-sternotomy care. As such, it has effectively become an accepted practice in the larger community and here at BCH as well, with surgeons, anesthesiologists, and families frequently requesting an ESB (unilateral or bilateral) as a part of the care they either provide or receive. We believe we have reached a point of clinical equipoise in relation to the existing standard of systemic opioid therapy and seek to evaluate the relative efficacy of this technique in a pediatric cardiac surgical population at BCH.

In order to best evaluate the efficacy of this block in the pediatric cardiac population, a blinded, randomized and controlled trial would be ideal. However, given that randomization could be challenging and the fact that blinding would not be feasible, we believe an observational prospective cohort study is most appropriate at this time.

As such, we propose to evaluate the comparative efficacy of BESB versus matched historical controls who received standard of care pain management (systemic opioid therapy) for patients undergoing cardiac surgery via sternotomy by means of a single arm, open label, interventional study that will compare as the primary outcome rescue analgesic requirements, rendered as opiate equivalents, at 12, 24 and 48 hours, and the 24 hour period preceding both 72 and 96 hours postoperatively. 'Efficacy' will be considered as a threshold of clinical significance being defined as a 15% difference). In addition to the primary endpoint, we plan to evaluate the duration of intubation, length of ICU stay, median pain scores, incidence of PONV (postoperative nausea and vomiting; 0-6h, 6-12h and overall), time to mobilization and adverse events between these groups. Postoperative data collected from standard clinical follow-up tools, such as return to baseline sleep and activity status as well as pain medication requirements at home, will also be compared. In addition, we plan to evaluate the quality of sleep and activity with a smart watch (Fitbit™) during the perioperative period in the BESB group only.

### **C. Preliminary Studies**

While the paravertebral block and, increasingly, the ESB are commonly used for postoperative management of numerous thoracic procedures in adults and children, there is little prospective data available evaluating the efficacy of these blocks in this population and no prospective data evaluating the utility of such blocks for management of post-sternotomy pain in a pediatric population.

Retrospective studies and case reports exist that suggest that ESBs are efficacious and low risk, but very few prospective data exist. The ESB has been described as having utility in the adult perioperative environment for patients undergoing breast surgery, shoulder surgery, thoracotomy/thoracoscopic surgery, thoracic spinal surgery, and ventral abdominal surgery. Two case reports have also described its utility in treating patients with chronic pain in the thoracic dermatomes. As noted above, there is at least one published prospective study in adults, but similar studies in pediatric patients are yet to be undertaken. In general, there is much less published evidence in children; however, there are case reports and case series describing its use for patients undergoing thoracic and abdominal surgery.

Large retrospective analyses of multiple pediatric regional anesthesia registries consistently report a very favorable safety profile for the provision of regional anesthetics in the pediatric population. A recent (2015) consensus statement from the American and European Societies of regional anesthesia (ASRA and ESRA) reported the risk profile of administering regional anesthetics to anesthetized children, citing a risk of postoperative neurologic symptoms of 0.93/1000 cases (>90% of which resolve completely within 1 month) and a rate of local anesthetic systemic toxicity of 0.08/10000 cases.

As previously noted, our group recently investigated the feasibility of performing BESBs in a pediatric cardiac surgical population undergoing sternotomy-based procedures at this institution. At the conclusion of this 10-patient pilot, we found that performing these blocks was technically feasible -- requiring 30 minutes or less of OR time -- and resulted in an approximate 25% reduction in rescue opioid requirements in the first 48 hours amongst the BESB group ( $p=0.048$ ). There were no significant adverse events noted during this pilot with the exception of a single instance of a kinked (but useable) catheter.

While the numbers at BCH are relatively small, retrospective analyses of ESBs performed in this institution in non-cardiac surgery have demonstrated no evidence that this block type is associated with any greater risk than that demonstrated by aggregate block data from the various pediatric regional anesthesia registries. Information currently available suggests that regional blockade, when performed properly, carries a very low risk of morbidity and mortality in appropriately selected infants and children. Furthermore, we have found no evidence of increased adverse events present in the ESB patients when compared to patients receiving other regional anesthetics in our local analysis. Indeed, two abstracts addressing the safety and efficacy of ESB blocks in BCH patients have recently been accepted for presentation at the major regional anesthesia conference.

## **D. Design and Methods**

### **(1) Study Design**

We propose a single arm, open label, interventional study to compare the opiate requirements of 45 patients who consent to receive BESB catheters following cardiac surgery via sternotomy versus 90 matched historical controls who had similar surgical procedures but without BESBs.

Patients meeting eligibility criteria will be recruited and enrolled to have BESBs placed for postoperative pain control as a part of their perioperative anesthetic

plan. These patients will subsequently have a variety of preoperative demographic and functional data collected as well as data related to their surgeries and postoperative course all collected for later analysis. This enrolled group of patients will subsequently be compared regarding these outcome measures with a 1:2 matched, retrospective analysis of patients in the cardiac surgical ERAS program who did not receive regional blocks as a component of their anesthetic care. (The ERAS Cardiac program is a heart center perioperative evidence-based quality initiative. Retrospective data analysis of outcomes for patients in this program is performed for quality improvement purposes and outcomes research [IRB P00029161 – PI: [name] MD, co-investigators: [name] MD, [name] MD]). Children aged 2 years through 17 years meeting entry criteria will be screened and recruited for participation from the Boston Children's Hospital cardiac surgical program.

## **(2) Patient Selection, Inclusion/Exclusion Criteria and Recruitment Method**

Patients from BCH who meet the criteria below will be considered for recruitment:

### **Inclusion Criteria:**

1. Scheduled as part of the cardiac surgical ERAS program: Patients scheduled for elective surgeries for the following congenital anomalies, or similar: atrial septal defects (all types), partial anomalous pulmonary venous connection (non-obstructed), cor-triatriatum, VSD, partial AV canal, sub-aortic membrane resection, anomalous aortic origin of the coronary arteries, and pulmonary valve/conduit implantation
2. Scheduled to undergo a first time surgical pulmonary valve or right ventricle to pulmonary artery conduit change in anatomic position, in the context of previous complete repair.
3. Ages 2 years through 17 years.

### **Exclusion Criteria:**

1. Single ventricle physiology.
2. Significant scoliosis or other anatomic contraindications to ESB.
3. Significant intraoperative hemodynamic instability or bleeding, as ascertained by clinicians taking care of the patient.
4. Patients with severe neurodevelopmental delays.

5. Patients with previous chronic pain syndromes.
6. Patients with a history of greater than 24 hours of postoperative or post-procedural opioid treatment at any point in the 2 months prior to surgery.
7. Lack of parental consent and/or child assent.

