### **(3) Description of Study Treatments or Exposures/Predictors**

Participants will have their medical record reviewed following enrollment for demographic information including: gender, age, weight and height, procedure, surgeon, and current and historical medication use.

Any other routine standard-of-care data will be collected preoperatively as well in addition to research-specific data points.

All enrolled patients will have bilateral erector spinae blocks (with catheters for postoperative local anesthetic infusion) placed by the by a member of the BCH regional anesthesia team (under the supervision of a member of the research team) in a sterile fashion after the cardiac surgical procedure is completed. The placement is as follows:

- The patient is placed in a lateral decubitus position (left or right), with all pressure points padded in routine fashion.
- The area for intervention is prepped with a chlorhexidine solution, and sterile drapes are applied to demarcate the block placement area.
- The T4/5 transverse process on one side is identified with the ultrasound transducer in a parasagittal orientation.
- An 18g Tuohy needle is advanced to the target area under direct ultrasound visualization. The needle tip is advanced until it contacts the transverse process, just below the erector spinae muscle complex.
- Normal saline is injected to confirm appropriate needle tip position. The erector spinae muscle is visualized to be elevated up off of the transverse process with normal saline injection
- With confirmation of appropriate needle tip position, the initial local anesthetic bolus is injected using a standard, weight-based dosing protocol.

- Following the bolus injection, a catheter is threaded into the space occupied by the local anesthetic bolus.
- Catheter tip position is verified by one or more of the following: ultrasound visualization of the catheter tip, ultrasound visualization of instilled normal saline and/or ultrasound visualization of a small hyperechoic (i.e. bright on ultrasound) injection of air.
- With the catheter tip position identified, the catheter is tunneled to a cutaneous exit point approximately 2-3cm from the incision using a Crawford needle.
- The catheter is dressed in standard fashion with an adhesive catheter anchor, Dermabond, Mastisol, Tegaderm and tape.
- This is repeated for the contralateral side. To the extent possible, this will be done without repositioning in a contralateral decubitus position.

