In addition to observational tools and subjective scoring, patient functional status (activity, sleep quality and other measures) will be assessed by actigraphic analysis using the Fitbit™ Charge 3 smartwatch. A Fitbit™ will be placed on the non-dominant arm, if possible, after extubation on the day of surgery. The Fitbit™ will remain on the patient until discharge from the hospital (which on average is about 5 days post-op) and the actigraphic data subsequently will be downloaded to the secure research database and the data wiped from the device. If a study subject had an unforeseeable complication and they no longer progressed along the standard recovery path (e.g. re-intubation, return to ICU), or if the watch was interfering in clinical care in any way, the Fitbit™ would be removed.

Following primary data collection for the enrolled subjects, each subject will be matched by surgical procedure using the STS procedure code, to 2 patients within the cardiac surgery ERAS program QI database (IRB #P00029161 which allows retrospective data analysis of outcomes) by the research team. All patients recruited for this study are themselves already part of the enhanced recovery after cardiac surgery clinical program [QIP]. Matching will be performed 1:2 with respect to surgical procedure and diagnosis using the STS codes, within 30% of the study patient's age and according to gender (if possible) and will be blinded to outcomes. Thus, up to 90 additional patients will be included in this study, retrospectively in addition to the 45 study patients from the single arm interventional cohort study (BESB).

Groups will be compared for demographic data, risk factors (from the STS database), diagnosis, procedure and cardiopulmonary bypass and clamp times to ensure their similarities

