### **Secondary:**

- Analgesic requirements, rendered as total opiate equivalents, at 12, 24 and 48 hours, and the 24-hour period preceding both 72 and 96 hours postoperatively.
- Duration of intubation following OR exit.
- Duration of ICU stay following OR exit.
- Duration of inpatient admission.
- Median pain scores collected per standard of care (VAS, NRS, INRS, or FLACC) at 0-3h, 3-6h, 6-12h, 12-24h, 24-36h and 36-48h.
- Incidence of postoperative nausea and vomiting during the following time ranges: 0-6h, 6-12h, 12-24h, and overall
- Time to mobilization (e.g. up to chair, ambulation).
- Quality/Quantity of mobilization and sleep via postoperative actigraphy.
- Outcome and satisfaction measures associated with routine perioperative questionnaire responses.
- Adverse events. – catheter, hemodynamic instability during placement (new inotrope or vasopressor – including Ca, volume > 5ml/Kg, variation 10% baseline SBP and MAP)
- All major Society of Thoracic Surgeons (STS) standard indices of morbidity and mortality

\*Of note, all of the above data points are collected automatically (via the electronic medical record) for all patients, as a part of their routine clinical care, regardless of whether or not they participate in the study.

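### The exclusion criteria, chiefly 3, 5 and 6, are not stated to apply to the historical controls, so the unadjusted opioid comparison could be biased by an unknown amount in an unknown direction

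*Combined protocol and SAP*

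**What the plan says.** Section D(2) opens with "Patients from BCH who meet the criteria below will be considered for recruitment", which ties the inclusion and exclusion lists to the prospective BESB cohort. Exclusion 3 is "Significant intraoperative hemodynamic instability or bleeding, as ascertained by clinicians taking care of the patient". Exclusion 5 is a prior chronic pain syndrome. Exclusion 6 is more than 24 hours of postoperative or post-procedural opioid treatment in the two months before surgery.

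The controls are described elsewhere. Section D(1) calls the comparison a "retrospective analysis of patients in the cardiac surgical ERAS program who did not receive regional blocks". Section D(3) gives the selection rule: "Matching will be performed 1:2 with respect to surgical procedure and diagnosis using the STS codes, within 30% of the study" patient's age, and by gender if possible, with the matching blinded to outcomes. After matching, "Groups will be compared for demographic data, risk factors (from the STS database), diagnosis, procedure and cardiopulmonary bypass and clamp times to ensure their similarities"; no action is stated if they differ.

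The block is placed "in a sterile fashion after the cardiac surgical procedure is completed" (Section D(3)). Section L names exclusions arising during surgery among the reasons for enrolling 45 BESB patients when 38 are needed. Section K compares opioid use by t-test, or by a rank-sum test if the data are not normal, with no covariates.

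**The concern.** Without randomisation, the comparison depends on selecting both groups by the same rules. Exclusion 3 matters most because it is not a baseline criterion. It can remove a consented BESB patient once the intraoperative course is known, on the treating clinicians' judgement. The BESB group is then conditioned on an operation without marked instability or bleeding; the controls, as described, are not. ERAS membership does not supply the same filter, because Section D(2) describes entry to the programme by the scheduled procedure.

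Exclusions 5 and 6 have a plausible link to opioid requirement, and neither is a matching variable. If patients covered by these three exclusions need more opioid and remain only among the controls, the comparison would favour BESB with no block effect. If they need less, it would work against BESB. Nothing in Section K would correct either.

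**Working it through.** **1. Each exclusion against the control rule**

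| Exclusion | Covered for controls by the stated rule? |
|---|---|
| 1 Single ventricle | Largely, through procedure and diagnosis matching |
| 2 Scoliosis or other anatomy | No, but little obvious link to opioid use |
| 3 Intraoperative instability or bleeding | No; bypass and clamp times may partly reflect it, but are only compared afterwards |
| 4 Severe neurodevelopmental delay | Not stated |
| 5 Chronic pain | No |
| 6 Recent opioid treatment | No |
| 7 Consent or assent | Cannot apply to retrospective controls |

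Age is a minor matter: the 30% window can leave the 2 to 17 range only at its edges (2 × 0.7 = 1.4 years; 17 × 1.3 = 22.1 years).

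**2. The plan's own figure.** Inputs from Section L: difference 0.18 in square-root total 96-hour OME, SD 0.32, two-sided 0.05, 80% power, 1:2. Normal formula: BESB n = (1.960 + 0.842)² × 0.32² × 1.5 / 0.18² = 37.2, so 74.4 controls, rounded up to 75. The t-based version gives 38 and 76 with power 80.1%. The stated 38/76 is reproduced and is not in dispute.

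**3. Size of a possible bias.** This is an illustration for the 96-hour sample-size endpoint only. It does not carry over to the other time points or to rescue-only use.

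Let f be the share of controls who would have been excluded, and s their mean shift in square-root OME. Bias = f × s. The documents give neither, so both are assumptions. I set s = 0.211, the ERAS group's SD in Table 2, because the shifted patients are controls. At the ERAS mean of 1.231, that shift means (1.442/1.231)² = 1.37 times the opioid use.

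- f = 2%: 0.02 × 0.211 = 0.004; 0.004/0.18 = 2% of target
- f = 5%: 0.05 × 0.211 = 0.011; 6% of target
- f = 10%: 0.10 × 0.211 = 0.021; 12% of target

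The bias reaches a tenth of the target (0.018) at a share of 0.018/0.211 = 8.5%. A zero shift gives no bias. A shift of −0.211 at 5% gives −0.011, against BESB.

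**4. Effect on the test.** I simulated 38 BESB and 76 controls with SD 0.32 and no true effect, moving each control by 0.211 with probability f, and applied the pooled t-test at two-sided 0.05 (600,000 runs). Two-sided error was about 5.0%, 5.2% and 6.0% for f = 2%, 5% and 10%. The rate of falsely finding BESB better, nominally 2.5%, was about 2.9%, 3.6% and 5.0%.

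**The case against.** The strongest reply is that this is silence, not contradiction. The opening section says that a complete protocol "consists of the CHeRP forms and the information provided in this form", and the ERAS database has its own protocol. Neither was available, and either may hold eligibility rules for controls. Section D(3) also describes the controls as included in the study, so the team may intend the criteria to cover them. This stands, and it lowers confidence. It does not supply the rule in the text that governs the matching.

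Second, there is real protection: one ERAS programme, matching on procedure and diagnosis, matching blinded to outcomes, and a planned comparison of STS risk factors and bypass and clamp times. This stands in part. Blinded matching prevents choosing controls by result, but does not equalise eligibility. The planned comparison does not name instability, bleeding, chronic pain or prior opioid use.

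Third, the effect may be negligible. At a 2% share it is essentially nil, and no document supports a larger share.

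Fourth, the consequence is limited: Section B accepts that a randomised trial would be ideal, and Section N presents this study as possible groundwork for one. That is fair, although a biased estimate could still misinform the design of that trial.

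**Conclusion.** The point holds as a gap in the control selection rule, at medium confidence, and it should be closed before controls are drawn. Followed as written, the plan removes BESB patients under exclusions 3, 5 and 6 and states no matching filter for controls, on an outcome tested without adjustment. Under the assumed shares of 2% to 10% and a shift of one control SD, the bias is 2% to 12% of the 0.18 target and two-sided error is about 5% to 6%.

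Three stronger readings are not supported:

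- **That the plan exempts controls from the exclusions.** It does not say so.
- **That the bias favours BESB.** This is plausible for chronic pain and recent opioid treatment, but the documents give no data on opioid use in such patients.
- **That the allowance for BESB losses, 7/45 = 15.6%, estimates the share of affected controls.** It covers every kind of BESB loss, including withdrawal and procedural changes, and says nothing about controls.

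**What to change.** In Section D(3):

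- State that candidate controls must meet the same age range and exclusions 1 to 6, as far as the record allows, before matching, judged blind to postoperative opioid data. If this is already the rule in the CHeRP forms or the ERAS database protocol, say so and cite it.
- Write one record-based definition of exclusion 3 and apply it to both groups. It classifies patients for analysis only; clinicians' decisions at surgery are untouched.
- Report the number removed in each group by criterion.

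Where consent and data permissions allow, add a sensitivity analysis comparing all consented BESB patients, block placed or not, with controls matched without the exclusion 3 filter. Section E says the listed outcomes are collected in routine care "regardless of whether or not they participate in the study". That describes collection, not permission to analyse, so the permission needs checking.

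The cost is chart screening, a somewhat smaller control pool (harder 1:2 matching for rare procedures) and a second match for the sensitivity analysis. Feasibility depends on what the database and medical record hold on instability, chronic pain and prior opioid use. The 38/76 is unchanged.
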